Multinational, controlled, prospective, active surveillance study that follows two cohorts. The cohorts consist of new users (starters³ and restarters⁴) of two different groups of hormonal contraceptives: FC Patch Low and COC_{LNG}. The study will use a non-interference⁵ approach to provide standardized, comprehensive, reliable information on these treatments in a routine clinical practice setting. Study participants will be enrolled via an international

² cf. Section 9.2.1

³ First ever user of a CHC

⁴ User who restarts hormonal contraceptive use with a CHC (same CHC as before or new CHC) after an intake break of at least two months.

⁵ I.e., 1) all new users of FC Patch Low or COC_{LNG} are eligible for enrollment if they give their informed consent; and 2) the physician's prescribing, diagnostic, or therapeutic decisions take place before study participants are recruited.

network of 2,000 – 3,000 CHC prescribing health care professionals. Study participants will be followed up for 24 months. All outcomes of interest will be captured by direct contacts between the investigator team and the study participants. Reported outcomes of interest will be validated via attending physicians and relevant source documents. The classification of outcomes of interest into ‘confirmed’ and ‘not confirmed’ will be verified by blinded independent adjudication.

Population

Approximately 101,000 study participants (50,500 FC Patch Low and 50,500 COC_{LNG} users) will be recruited via a network of 2000 – 3000 CHC-prescribing health care professionals (e.g. gynecologists and general practitioners) in approximately 6 European countries. All starters and restarters (see above) of FC Patch Low or COC_{LNG} who are willing to participate in the study are eligible for enrollment into the study⁶.

Variables

Primary statistical variable: VTE hazard ratio for FC Patch Low vs. COC_{LNG} adjusted for age, BMI, duration of current use and family history of VTE. Results are based on patient-reported VTE that will be validated via the attending physicians and medical records. Other variables include arterial thromboembolism, cancer, pregnancy related data, application site reactions and serious adverse events.

Data sources

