9.1 Study design

This is a large, multinational, controlled, prospective, active surveillance study that follows two cohorts. The cohorts consist of new users (starters¹⁴ and restarters¹⁵) of two different groups of hormonal contraceptives: FC Patch Low and COC_{LNG}. The study will use a non-interference¹⁶ approach to provide standardized, comprehensive, reliable information on these treatments in a routine clinical practice setting.

Study participants will be recruited via an international network of 2,000 – 3,000 contraceptive-prescribing health care professionals (e.g. gynecologists and general practitioners). It is expected to recruit the 101,000 participating women within 60 months. However, if the actual recruitment is not in line with the recruitment plan, alternatives will be sought to improve recruitment rates. This includes, but is not limited to the expansion to other non-EU countries (e.g. Latin America), contacting of gynecological associations to recommend study participation for physicians or including other prescribing health care professionals. After study entry, study participants will be followed for a period of 12 to 24 months for rare serious safety outcomes. Regular, active contacts with the study participants by the ZEG study team (= active surveillance) will provide the necessary information on health-related events or changes in health status. Additional follow-up procedures (cf. Section 9.2.4) will be used to validate self-reported events.

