All study participants will be contacted at 6, 12 and 24¹⁷ months after study entry. By means of these contacts, almost all relevant clinical outcomes will be captured. However, laypersons often misclassify adverse events (e.g., pneumonia as “pulmonary embolism” or migraine attacks as “stroke” even if modern imaging procedures do not provide any indication of the perceived event). This type of inaccuracy in patient reports will require careful validation of the reported events. This will be accomplished by contacting the relevant physicians and by reviewing relevant source documents. Under routine medical conditions, clinical outcomes are not always confirmed by diagnostic procedures with high specificity. Therefore, reported serious clinical outcomes have to be classified as “confirmed” or “not confirmed” by ZEG physician(s) according to a predefined algorithm (cf. Section 9.10.1). At the end of the study this classification will be verified by blinded independent adjudication (cf. Section 9.10.2).

¹⁴ First ever user of a CHC

¹⁵ User who restarts hormonal contraceptive use with a CHC (same CHC as before or new CHC) after an intake break of at least two months.

¹⁶ I.e., 1) all new users of FC Patch Low or COC_{LNG} are eligible for enrollment if they give their informed consent; and 2) recruitment of study participants should not influence the physician’s prescribing, diagnostic, or therapeutic decisions.

¹⁷ Or at the end of the study if the study ends prior to the 24 month follow-up of an individual patient.

The study will be conducted in approximately 6 European countries.

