9.2.2 Selection of Study Population

Approximately 50,500 FC Patch Low users and 50,500 users of COC_{LNG} (including adolescents) will be recruited by participating physicians. Overall, 101,000 study participants are needed in order to provide approximately 150,000 woman-years (WY) (cf. Section 9.5), assuming a drop-out rate of approximately 0.7% per month.

Recruitment of study participants will be conducted via existing networks of contraceptive-prescribing health care professionals (e.g. gynecologists and general practitioners) who have participated in similar cohort studies in the past. Physicians will recruit FC Patch Low and

COC_{LNG} users in a 1 to 1 ratio. It is expected that this ratio reflects approximately the ratio of starter and restarter prescriptions of FC Patch Low and COC_{LNG} under routine clinical conditions. Only after the decision of the contraceptive prescription has taken place, the physician may ask the woman for study participation. For every FC Patch Low user recruited, the physician has to recruit the next new COC_{LNG} user (starter or restarter) who is willing to participate in the study.

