9.7 Data analysis

Based on available data and pharmacological considerations the *a priori* assumption is that use of FC Patch Low is not associated with an increased risk of VTE compared to COC_{LNG}. That is, a statistical comparison of FC Patch Low and COC_{LNG} is not expected to show a difference. Therefore, a non-inferiority design was chosen to investigate the VTE risk of FC Patch Low. The primary analysis will be based on the comparison of the upper confidence limit for the point estimate of the VTE²² hazard ratio with the predefined non-inferiority limit (see below).

The final analyses will include both an “as treated” (AT) and an intention-to-treat (ITT) analysis using Cox regression models. The safety conclusions of the study, however, will be based on the AT analyses (outcomes of interest will be assigned to the treatment she used at the time of the event) because the ITT approach (outcomes of interest are assigned to the treatment which was prescribed at study entry) potentially dilutes differences between treatments.

Incidence rates, incidence rate ratios (HRs), excess risks, as well as crude and adjusted hazard ratios will be calculated. The appropriate confounding variables will be built into the model. Based on the expectation of a small absolute number of serious outcomes of interest the number of confounding variables will be limited to well-established risk factors for these outcomes (e.g., age, BMI, duration of current use, and VTE history). The final decision on the confounding variables will be made by the Safety Monitoring and Advisory Council before the first interim analysis of follow-up data. In addition, alternative analysis will be performed with other potential baseline risks to check the appropriateness of this decision. Similar analyses will be performed for all VTE (cf. Section 8) and arterial thromboembolism (e.g., acute myocardial infarction and stroke), the other secondary variables and other serious adverse events.

The null hypothesis to be tested is: $HR_{VTE} \geq 1.5$ (i.e., the VTE hazard ratio for FC Patch Low vs. COC_{LNG} is higher than or equal to 1.5). The alternative hypothesis is: $HR_{VTE} < 1.5$.

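### The stated primary adjustment set omits country, and 1:1 recruitment by physician does not protect the as-treated person-time on which the safety conclusions rest

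*Protocol*

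**What the plan says.** The abstract (Variables) gives the primary hazard ratio as "adjusted for age, BMI, duration of current use and family history of VTE", with no wording that marks the list as examples. Section 9.7 gives a similar list as examples ("e.g., age, BMI, duration of current use, and VTE history"). It adds that "the number of confounding variables will be limited to well-established risk factors for these outcomes", because few outcomes are expected.

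Neither list contains country. Nor is country named among the risk factors in Section 9.3.1, the stratification by time of exposure and the example sub-analyses in Section 9.7, or the stratified analyses in Section 9.9.

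On geography, Section 9.1 states: "The study will be conducted in approximately 6 European countries". If recruitment lags, the same section allows "the expansion to other non-EU countries (e.g. Latin America").

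On balance, Section 9.2.2 has each physician recruit the next willing new LNG user for every patch user. It adds: "It is expected that this ratio reflects approximately the ratio of starter and restarter prescriptions". Section 9.7 bases the safety conclusions on the as-treated analysis.

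The set can still change. Section 9.7 states: "The final decision on the confounding variables will be made by the Safety Monitoring and Advisory Council before the first interim analysis of follow-up data". It also says that "alternative analysis will be performed with other potential baseline risks to check the appropriateness of this decision".

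**The concern.** The rate of confirmed VTE can differ between countries, because the endpoint depends partly on local diagnostic practice. Section 9.10.1 accepts a probable VTE without imaging if a health professional confirms the diagnosis, and Section 9.10.2 counts an event as confirmed if one of three adjudicators does. If patch time and LNG time are also spread differently over countries, country confounds the hazard ratio.

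The 1:1 rule limits this at entry but not afterwards. Women may stop, restart or switch at any time (Section 9.2.2), and as-treated time follows the product actually used. If patch persistence relative to LNG persistence differs between countries, the person-time drifts out of balance.

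Two errors are possible. If patch time lies more in low-rate countries, the hazard ratio is pulled down and non-inferiority may be declared wrongly. If it lies more in high-rate countries, power is lost. Section 9.9 argues that diagnostic bias should not lead to an underestimate of the patch risk, but that argument concerns heightened awareness of a new product, not differences in detection between countries.

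**Working it through.** **Inputs from the protocol (Sections 9.5 and 9.7).** Margin 1.5, one-sided alpha 0.05, power 0.80, true hazard ratio 1.0, 150 events, overall rate 10 per 10,000 woman-years (WY), equal cohorts.

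**The plan's own figure.** Events needed = 4 × (1.645 + 0.842)² / (ln 1.5)² = 150.4, which rounds up to 151 and agrees with the stated 150. With 150 events:
- SE of the log hazard ratio = 2/√150 = 0.163.
- Power = Φ(ln 1.5/0.163 − 1.645) = 79.9%.
- At an estimate of 1.0, the one-sided 95% upper limit is exp(1.645 × 0.163) = 1.31.
- Non-inferiority needs an estimate of at most 1.5/1.308 = 1.147.

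The planned power has no slack.

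**Formulas.** If country is ignored, the hazard ratio is multiplied by approximately

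B = Σ(patch share of time × country rate) / Σ(LNG share of time × country rate).

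Then power = Φ((ln 1.5 − ln B)/0.163 − 1.645), and error at a true hazard ratio of 1.5 = Φ(−ln B/0.163 − 1.645).

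**Scenario 1: 1:1 entry holds, persistence differs.** Assumptions (not in the protocol): six equal countries with rates 5, 7, 9, 11, 13 and 15 per 10,000 WY (mean 10). LNG time is spread evenly. The patch-to-LNG time ratio changes linearly across countries around 1.0, with a total spread of 20 or 50 percentage points.

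- Spread 20 points: ratios run from 0.90 to 1.10. The mean product of the deviations is 2 × (5 × 0.10 + 3 × 0.06 + 1 × 0.02)/6 = 0.233, and 0.233/10 = 0.023, so B = 1.023.
- Spread 50 points: 2 × (5 × 0.25 + 3 × 0.15 + 1 × 0.05)/6 = 0.583, so B = 1.058.
- If the gradient runs the other way, B = 0.977 and 0.942.

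| Spread | B, patch time toward high-rate countries | Power | B, patch time toward low-rate countries | Error at true HR 1.5 |
|---|---|---|---|---|
| 0 | 1.000 | 79.9% | 1.000 | 5.0% |
| 20 points | 1.023 | 75.7% | 0.977 | 6.7% |
| 50 points | 1.058 | 68.8% | 0.942 | 10.1% |

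**Scenario 2: a 55/45 split of time.** Assumptions: two country groups with rates 5 and 15; 55% of patch time but 45% of LNG time lies in the low-rate group. Then B = (0.55 × 5 + 0.45 × 15)/(0.45 × 5 + 0.55 × 15) = 9.5/10.5 = 0.905, and the error at a true hazard ratio of 1.5 is 15.1%. In the opposite direction B = 1.105 and power is 58.9%.

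**How likely is scenario 2?** Starting from 1:1 entry, the patch-to-LNG time ratio must be 55/45 in one group and 45/55 in the other. Relative persistence must then differ (55/45)² = 1.49-fold between the groups, unless the 1:1 ratio was not kept.

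**Expected decisions in scenario 2.** With a true hazard ratio of 1.0 and B = 1.105, the expected upper limit is 1.105 × 1.308 = 1.45, still below 1.5. With a true hazard ratio of 1.5 and B = 0.905, the estimate is 1.36 and the upper limit 1.78, still above 1.5. The probabilities shift; the expected decision does not.

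**The case against.** The strongest reply is that the covariate set is not final. The list in Section 9.7 consists of examples, and the Safety Monitoring and Advisory Council decides before the first interim analysis of follow-up data. Section 9.3.1 promises to test all potential confounders in a multivariable model, alternative covariate analyses are planned, and details go to a later analysis plan. This stands in part: country can still be added. But the abstract gives a definite list, no section mentions country, and limiting the set to well-established risk factors steers away from it. The reason for that limit, few events, does not apply to stratification, which estimates no extra coefficient.

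The second reply is that 1:1 recruitment by physician balances countries. At entry it largely does. Differences in persistence by product alone, or by country alone, then do no harm; confounding needs a product-by-country difference that lines up with VTE rates. This stands, and it is why scenario 1 is the realistic one. Two reservations remain. Sections 9.2.2 and 9.2.3 also say that all eligible women are to be asked, which sits uneasily with a fixed ratio. And Table 1 with its footnote already deducts 11% for loss to follow-up and within-study switchers, so person-time is expected to depart from enrolment.

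Third, the formula is a ratio of crude rates. Section 9.9 expects excess VTE risk in the first months of use, when the entry balance is best preserved, and the Cox model accounts for duration of use. The formula therefore tends to overstate bias that arises through persistence. The planned intention-to-treat analysis, which largely keeps the entry balance, would also help to reveal such an artefact. Both points are fair, but neither puts country into the primary analysis.

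**Conclusion.** The point holds as a modest weakness with an almost free remedy. The stated primary adjustment set leaves out country, and the routes by which it might be added do not secure it. Under 1:1 entry and the assumptions of scenario 1, the bias is about 2 to 6%. Power falls from 80% to about 76 to 69%, or the one-sided error rises from 5% to about 7 to 10%, depending on direction. A 55/45 split would be worse (error 15% or power 59%), but needs a strong product-by-country difference in persistence or failure to keep the 1:1 ratio. All country rates, persistence differences and splits are assumptions; the protocol gives none.

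A reader might infer that a modest imbalance by country would by itself carry the hazard ratio or its confidence limit across 1.5. The figures do not support that: even with a threefold rate difference and a 55/45 split, the expected upper limit at a true hazard ratio of 1.0 is 1.45. A small bias changes the conclusion only when the estimate is already near 1.15. Nor does the protocol rule country out for good, since the covariate decision is still to be made.

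**What to change.** In the abstract and in Section 9.7, state that the primary Cox model is stratified by country, with a separate baseline hazard per country and a common hazard ratio. Make any added non-EU country or region its own stratum. Keep the named covariates as they are for this purpose, and report person-time and VTE rate by country and cohort, so that any drift from the 1:1 balance can be seen.

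The country of participation is already known, so no new data are needed. With about 6 strata and 150 events (about 25 per stratum on average) the loss of precision is negligible. Stratification also brings the analysis closer to the within-physician recruitment scheme.

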9.1 Study design

This is a large, multinational, controlled, prospective, active surveillance study that follows two cohorts. The cohorts consist of new users (starters¹⁴ and restarters¹⁵) of two different groups of hormonal contraceptives: FC Patch Low and COC_{LNG}. The study will use a non-interference¹⁶ approach to provide standardized, comprehensive, reliable information on these treatments in a routine clinical practice setting.

Study participants will be recruited via an international network of 2,000 – 3,000 contraceptive-prescribing health care professionals (e.g. gynecologists and general practitioners). It is expected to recruit the 101,000 participating women within 60 months. However, if the actual recruitment is not in line with the recruitment plan, alternatives will be sought to improve recruitment rates. This includes, but is not limited to the expansion to other non-EU countries (e.g. Latin America), contacting of gynecological associations to recommend study participation for physicians or including other prescribing health care professionals. After study entry, study participants will be followed for a period of 12 to 24 months for rare serious safety outcomes. Regular, active contacts with the study participants by the ZEG study team (= active surveillance) will provide the necessary information on health-related events or changes in health status. Additional follow-up procedures (cf. Section 9.2.4) will be used to validate self-reported events.

All study participants will be contacted at 6, 12 and 24¹⁷ months after study entry. By means of these contacts, almost all relevant clinical outcomes will be captured. However, laypersons often misclassify adverse events (e.g., pneumonia as “pulmonary embolism” or migraine attacks as “stroke” even if modern imaging procedures do not provide any indication of the perceived event). This type of inaccuracy in patient reports will require careful validation of the reported events. This will be accomplished by contacting the relevant physicians and by reviewing relevant source documents. Under routine medical conditions, clinical outcomes are not always confirmed by diagnostic procedures with high specificity. Therefore, reported serious clinical outcomes have to be classified as “confirmed” or “not confirmed” by ZEG physician(s) according to a predefined algorithm (cf. Section 9.10.1). At the end of the study this classification will be verified by blinded independent adjudication (cf. Section 9.10.2).

¹⁴ First ever user of a CHC

¹⁵ User who restarts hormonal contraceptive use with a CHC (same CHC as before or new CHC) after an intake break of at least two months.

¹⁶ I.e., 1) all new users of FC Patch Low or COC_{LNG} are eligible for enrollment if they give their informed consent; and 2) recruitment of study participants should not influence the physician’s prescribing, diagnostic, or therapeutic decisions.

¹⁷ Or at the end of the study if the study ends prior to the 24 month follow-up of an individual patient.

The study will be conducted in approximately 6 European countries.

9.2 Setting

The study will be conducted by the Berlin Center for Epidemiology and Health Research (ZEG).

The study will be divided into 2 phases: a baseline survey, which includes an initial consultation at baseline with a participating physician, and a follow-up phase, which includes two follow-up contacts within the first year, and then a follow-up at 24 months after study entry. The follow-up phase will end approximately one year after enrollment of the last study participant. Participants who are enrolled within the last year of the recruitment phase will have their last follow-up at the end of the follow-up phase (between 12 and 24 months after study entry). Follow-up contacts are calculated in calendar months and years following the baseline visit.

Additionally to the baseline questionnaire, a registry will be implemented to document all eligible non-participating women in an anonymized way.

The study will be overseen by an independent committee of experts, the Safety Monitoring and Advisory Council (SMAC), who will review the study data every 6 months and on request of the Principal Investigator.

9.2.1 Treatments

- Cohort 1:** FC Patch low, a transdermal patch containing 2.1mg of gestodene and 0.55mg of ethinyl estradiol
- Cohort 2:** Levonorgestrel-containing COCs: 1) monophasic preparations containing 20 – 30mcg of ethinylestradiol; 2) multiphasic preparations containing up to 40mcg of ethinylestradiol

9.2.2 Selection of Study Population

Approximately 50,500 FC Patch Low users and 50,500 users of COC_{LNG} (including adolescents) will be recruited by participating physicians. Overall, 101,000 study participants are needed in order to provide approximately 150,000 woman-years (WY) (cf. Section 9.5), assuming a drop-out rate of approximately 0.7% per month.

Recruitment of study participants will be conducted via existing networks of contraceptive-prescribing health care professionals (e.g. gynecologists and general practitioners) who have participated in similar cohort studies in the past. Physicians will recruit FC Patch Low and

COC_{LNG} users in a 1 to 1 ratio. It is expected that this ratio reflects approximately the ratio of starter and restarter prescriptions of FC Patch Low and COC_{LNG} under routine clinical conditions. Only after the decision of the contraceptive prescription has taken place, the physician may ask the woman for study participation. For every FC Patch Low user recruited, the physician has to recruit the next new COC_{LNG} user (starter or restarter) who is willing to participate in the study.

Subjects will be considered for enrollment in this study after the participating physician has determined that FC Patch Low or COC_{LNG} use is appropriate. There will be no specific medical inclusion/exclusion criteria and no age restrictions. However, women who 1) have been pregnant within 3 months before treatment initiation or 2) have a history of cancer/chemotherapy or an increased genetic risk for VTE at baseline will be excluded from the analysis of VTE. All women who are eligible are to be asked by their physician if they are willing to participate. As this is a non-interventional study, the possibility to participate in the study should not be discussed with the study participant before both - physician and study participant - agree upon the prescription. The physician is to explain the nature of the study, its purpose and associated procedures, and the expected duration of follow-up for each woman prior to her entry into the study. Each woman is to have ample opportunity to ask questions and must be informed about her right to withdraw from the study at any time without disadvantage and without having to provide reasons for her decision. This information will be provided on an informed consent and data privacy form, which must be signed by all study participants. This study has no age restrictions and adolescents can be asked for participation in countries where no ethical or regulatory restrictions for that age group exist. As adolescents are a specifically protected group, local law might require a parent's or guardian's signature, which will then additionally to that of the adolescent study participant be provided on the informed consent form. All documents are to be approved by the relevant local Ethics Committees and the relevant Data Privacy Office, if applicable.

Once enrolled, a study participant may discontinue (and restart) use of hormonal contraception or may switch to another hormonal contraceptive at any time. However, subjects will continue to be followed whether or not they remain on the prescribed contraceptive, provided that they do not withdraw their consent. For the primary analysis outcomes of interest/adverse events will be assigned to the treatment at the time the outcome/event occurred. During the follow-up phase, subjects will be asked whether they have discontinued contraceptive use. Information on the date and reason for discontinuation during the follow-up phase will also be collected.

